7.6 Pregnancy

Pregnancy is not an AE unless it results in congenital anomaly or birth defect, in which case it is a SAE. If the partner of a male patient should become pregnant while he is participating in the study, the patient should inform his treating physician immediately. All pregnancies must be reported at once to the principal investigator and medical monitor. All confirmed pregnancies will be followed until birth or until voluntary or spontaneous termination.

8. OUTCOME ASSESSMENT

8.1 Radical Prostatectomy Specimen

Most of the study outcomes in this immunologic trial will depend on collection of prostate tissue from prostatectomy specimens. All pathologic specimens will be handled in routine fashion by the operating room (OR) staff, except that as soon as the specimen is removed the OR nurse will directly page a tissue harvesting technician that is part of the Brady Urological Research Institute Prostate Specimen Repository Team. Accessioning of pathology specimens will be coordinated in the OR areas by the Departments of Urology and Pathology. A study technician will be available to the pathologist receiving the specimen to assure that the tissue is handled appropriately for the intended bioassays. At the time of harvesting, the pathologist will apply ink and cut the prostate specimen in transverse sections. The specimen will be fixed in 10% phosphate buffered formalin, and tissue blocks will be paraffin-embedded and sectioned at 4 µm thickness for routine histologic evaluation and for immunohistochemical determinations. Fixation should occur as soon as possible after operative removal of the prostate, and ideally within 30-60 minutes. Assessment of index tumors for Gleason grade, nodal involvement, and pathologic staging will be conducted in usual fashion and will be provided to the patient for prognostic information. After the pathology report is available. a database will be established and all information from the pathology reports of all

samples will be included. Tumor blocks and/or additional unstained slides will be collected for study-specific quantitative immunohistochemical evaluations.

8.2 **Primary Endpoint**

8.2.1 Analysis of M2-TAM infiltration

The primary measure of treatment effect in this study will be achieved by quantification of M2-TAMS in prostate tumor specimens of treated patients. Tissue microarrays (TMAs) from formalin-fixed tumor samples will be analyzed for the degree of TAM infiltration using immunohistochemical staining for CD206 (28, 29). Analyses will be performed in the laboratory of [name]. The contact information for the [name] laboratory is listed below:

[name], PhD [name] [name] 21231 [contact] [contact] Email: [contact]

8.3 Secondary Endpoints

8.3.1 Rate of adverse events

All subjects receiving at least one dose of the study drug will be evaluated for safety by monitoring symptoms, physical examinations, and laboratory tests. Adverse events will be classified and graded according to the NCI Common Toxicity Criteria version 4.0 (see Appendix B). The absolute number and frequency of each adverse event will be reported, and subdivided according to toxicity grade. A description of adverse events by treatment arm will also be reported. A particular adverse event occurring more than once in the same subject will be counted only once and at its worse grade.

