5. STUDY PLAN

5.1 Overview and Schema

This is a single-center, single arm, open-label phase II study evaluating the safety, antitumor effect, and immunogenicity of neoadjuvant DUPILUMAB given prior to radical prostatectomy in men with high-risk localized prostate cancer. Patients will be recruited from the outpatient Urology clinic. Men will be treated with dupilumab 600 mg s.q. on day 1, and then 300 mg s.q. on days 8, 15, 22, 29, 36, 43. They will then undergo surgery on day 57. 14 days after the last dose of Dupilumab, prostate glands will be harvested at the time of radical prostatectomy, and prostate tissue will be examined for the secondary endpoints. Follow-up evaluation for adverse events will occur 30 days and 60 days after surgery. Patients will then be followed by their urologists according to standard institutional practices, but will require PSA evaluations every 3 (\pm 1) months during year 1 and every 6 (\pm 2) months during years 2-3.

Table 1STUDY CALENDAR

Every effort should be made to keep visits, tests, and procedures on schedule. Acceptable deviations are listed below.

	Screening Evaluationª	Treatment Days (1, 8,15, 22, 29, 36, 43) (+/- 1 day)	Radical Prostatectomy Day 57 (+/- 3 days)	Follow-up, 30, and 60 Days Post-op (+/- 1 wk) ^{h,i}	LTFU (+/- 1 Month) ⁱ
Informed consent	Х				
Medical history	Х				
Review of medications	Х	Х	х	х	
Physical examination	Х	Х			
Vital signs	Х	Х	х		
Height and weight	Х	Х	х		
Performance status	Х	Х	х	х	
CT and bone scan ^b	(X)				
Hematology labs, coagulations ^c	х	х	Х	х	
Chemistry labs ^d	Х	Х	х	Х	
Serum PSA ^e	Х		х	Х	Х
DUPILUMAB dose		Х			
Toxicity assessment	X			X	
Surgical specimen ^f			Х		
Pathologic review ^g	Х		Х		

a: The screening (pre-treatment) evaluation should be conducted within 42 days (±4 days) of starting protocol therapy.

b: Staging CT (if allergic to CT scan contrast, obtain MRI with contrast) and bone scans should only be performed if clinically indicated, and are not mandatory.

c: Hematology laboratories include hemoglobin, hematocrit, white blood cell count with differential (including absolute eosinophil count), and platelets. In addition, prothrombin time (PT/INR) and activated partial thromboplastin time (APTT) should be checked at screening, then as clinically indicated.

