7.4 Perioperative Adverse Events

Complications of surgery or those occurring in the early post-operative period will be recorded. These include wound complications, estimated blood loss, post-operative infections, delayed wound healing, abnormal laboratory values, etc. Duration of hospital stay will be recorded. Additional medical examinations will be allowed at the request of patients during drug administration or at the discretion of the principal investigator for the evaluation of new adverse events that warrant physical examination. During and following completion of the study, patients should notify the study staff of any problems that occur between visits or following study termination by telephone and, if necessary, will be evaluated by the investigator or study personnel at an unscheduled interim visit.

Operative/perioperative events will be recorded as described in Section 7.1, and their severities will be categorized using the NCI CTCAE version 4.0 criteria. The relationship of these events to the investigational drug(s) will be determined by the principal investigator together with urologist co-investigators and, if necessary, with the primary urologic surgeon. Reporting of these events will follow the same guidelines described in Section 7.5.

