Power. For the primary outcome of pre- vs. post-treatment decrease in M2-TAM infiltration, power is based on the paired t-test. With 20 patients, we have the power (\geq 81%) to detect a decrease of \geq 0.67 standard deviation unit (effect size = 0.67) (14). This is likely to be conservative as we observed a much larger difference in M2-TAM levels between primary and metastatic tumors in our data. Power calculated using PASS v. 11 (NCSS Software, Kaysville, UT). The continuous toxicity monitoring design with n=20 above has probability = 0.048 of early stopping if the Grade \geq 3 AE rate is <15%. Toxicity boundaries calculated using software developed by Ivanova (13)

(http://cancer.unc.edu/biostatistics/program/ivanova/ContinuosMonitoringForToxicity.aspx)

Frequency, types, and grades of adverse events in each treatment group will be measured using the NCI Common Toxicity Criteria version 4.0, and will be summarized using descriptive statistics. Formal safety assessments will be performed from the time of first administration Dupilumab until the 60th postoperative day.

10.1.2: **Early stopping rule for feasibility:** We do not anticipate an increase in the surgical difficulty with the use of neoadjuvant DUPILUMAB. Men who have had acute (post-biopsy) and prolonged issues (chronic prostatitis) with prostate infection/inflammation are fairly routine in urologic surgical practice, and we anticipate that the immune infiltrate potentially induced by DUPILUMAB would not pose a substantial increase in surgical difficulties. However, in addition to safety, feasibility will be monitored separately. The feasibility rule for this study will be based on a change in surgical outcomes beyond what may be expected for patients without presurgical interventions and that may be attributable to the study drug. These events would include: (1) average blood loss in excess of 2500 mL, (2) average operative time in excess of 3.5 hours, and (3) average hospital stay in excess of 4 days. These values are

approximately 2 standard deviations above the average surgical outcomes for men undergoing radical prostatectomy at Johns Hopkins Hospital.

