10.4 Safety Analysis

10.4.1 Evaluation of adverse events

Treatment-emergent adverse events will be translated from investigator terms to MedDRA version 6.0 terminology and summarized (number and percentage of patients) for all patients who receive at least one dose of the study drug(s). Adverse event summaries will be organized by body system, frequency of occurrence, intensity (*i.e.*, severity grade), and causality or attribution. Patients who experience an adverse event more than once will be counted only once. The occurrence with the maximum severity will be used to calculate intensity.

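### The once-at-worst-grade rule for adverse events pools dosing with the 60 days after prostatectomy, so the by-grade table mixes surgical and on-drug severity and the attribution of repeated events is left open

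*Combined protocol and SAP*

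**What the plan says.** Section 8.3.1 describes the main adverse-event table: "The absolute number and frequency of each adverse event will be reported, and subdivided according to toxicity grade". It then gives the counting rule: "A particular adverse event occurring more than once in the same subject will be counted only once and at its worse grade".

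Section 10.4.1 also counts a patient once for a repeated event and adds: "The occurrence with the maximum severity will be used to calculate intensity". Its summaries are organised by body system, frequency, intensity and causality. They cover treatment-emergent events, a term the plan does not define.

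Section 10.1 fixes one window: "Formal safety assessments will be performed from the time of first administration Dupilumab until the 60th postoperative day". On the timing of prostatectomy, Section 5.1 says: "They will then undergo surgery on day 57". The study calendar allows 3 days either side, and the last dose falls on day 43.

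Section 7.4 puts surgical events through the same process: "Operative/perioperative events will be recorded as described in Section 7.1, and their severities will be categorized using the NCI CTCAE version 4.0 criteria". Its examples include postoperative infections and abnormal laboratory values. On causality it says: "The relationship of these events to the investigational drug(s) will be determined by the principal investigator together with urologist co-investigators".

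No section divides the adverse-event tables at surgery.

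**The concern.** Safety and tolerability of dupilumab is a secondary objective (Section 1.2). The trial has one arm, and every man evaluable for efficacy has a major operation shortly after his last dose. With no control group, timing and attribution are the only means of separating what the drug does from what the operation does. A worst-grade rule that runs across both periods discards timing for any term that occurs in both. Laboratory terms are obvious candidates, because the study calendar schedules hematology and chemistry on dosing days, on the day of surgery and at both postoperative visits.

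At stake is how the descriptive safety tables read. A term that was mild during dosing may appear at the grade it reached after surgery. Two analysts could also obtain different drug-related counts from the same data, because the plan does not say which occurrence supplies the attribution.

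**Working it through.** **1. The plan's own figure.** The plan attaches no number to this rule. The nearest adverse-event figure is the 0.048 probability of early stopping in Section 10.1. It reproduces: an exact binomial recursion over the printed boundary, with a 15% event rate and 20 patients, gives 0.04796. It does not enter the argument below.

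**2. How much of the window is postoperative.** Inputs: first dose day 1, surgery day 57 (range 54 to 60), window end at postoperative day 60.
- Surgery day 57: the window ends on day 57 + 60 = 117. Before surgery 57 − 1 = 56 days, after surgery 60 days, and 60/116 = 51.7%.
- Surgery day 54: 60/(53 + 60) = 53.1%.
- Surgery day 60: 60/(59 + 60) = 50.4%.

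About half the window follows surgery. Section 7 defines an adverse event as arising during the study or within 30 days post-treatment. If an analyst ended the tables 30 days after the last dose, that would be day 43 + 30 = 73, which is postoperative day 16 (13 to 19 over the allowed surgery range). The window would still straddle surgery.

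**3. The rule applied to one man.** Suppose the same term occurs at Grade 2 during dosing, scored related, and at Grade 3 after surgery, scored unrelated.
- By-grade table, Section 8.3.1: one count, at Grade 3. The on-drug Grade 2 is not shown. The man is still counted for the term.
- Causality summary, Section 10.4.1: one count, with intensity Grade 3. The text does not say whether the attribution is related or unrelated, nor whether once means once overall or once within each causality category.

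**4. Scale, by assumption only.** The documents give no rates, so these are illustrations.

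(a) Let a be the share of men with a term on drug and b the share who, independently, have it at a higher grade after surgery. Expected men affected = 20 × a × b.
- a = b = 10%: 20 × 0.10 × 0.10 = 0.2
- a = b = 30%: 20 × 0.30 × 0.30 = 1.8

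(b) Suppose 6 of 20 men (30%) have a related event of a term on drug, 70% at Grade 1 and 30% at Grade 2. A share q of them have the same term, unrelated, after surgery, split 40/45/15% over Grades 1/2/3.
- Chance that the later grade is higher: 0.70 × (0.45 + 0.15) + 0.30 × 0.15 = 0.465.
- Chance that it is higher or equal: 0.70 × 1.00 + 0.30 × (0.45 + 0.15) = 0.88.

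| q | On-drug grade replaced (0.465q) | Men out of 6 | Higher or equal (0.88q) |
|---|---|---|---|
| 25% | 12% | 0.7 | 22% |
| 50% | 23% | 1.4 | 44% |
| 75% | 35% | 2.1 | 66% |

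The second and third columns apply to the by-grade table. Related events would be lost from the causality summary only if an analyst also took attribution from the worst occurrence. On that reading, at q = 50%, the related rate would fall from 30% to 30% × (1 − 0.2325) = 23% if ties keep the related record, or to 30% × (1 − 0.44) = 17% if they do not.

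**The case against.** A reader might infer that the rule erases drug-related events: a man with a related Grade 1 event on drug and an unrelated Grade 2 recurrence after surgery would be tabulated as Grade 2, unrelated. The documents do not support that. Section 10.4.1 ties the worst occurrence to intensity and to nothing else. Counting the man once in a related-events summary is fully compatible with its text, and the Section 8.3.1 table has no stated attribution column. This part of the objection stands, and the point on causality is only that the text leaves it open.

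A reader might also infer that nothing else in the plan could recover the on-drug event. That is too strong. Every event is documented on the case report form (Section 7.1.1) with causality judged by the investigator (Section 7.1.3). Abnormal laboratory parameters are summarised separately (Section 10.4.3). Serious events and those leading to early withdrawal or death have their own summary (Section 10.4.2). What remains uncovered is the planned tabulation of non-serious, non-laboratory events at lower grades.

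It is also fair to say that a postoperative event is not automatically unrelated. Section 2.2.1 gives median times of 10 and 13 weeks from the last steady-state dose to undetectable drug. This schedule ends before the Week 16 steady state, so those figures do not transfer directly, but drug may still be present at surgery 14 days after the last dose. Period is therefore no substitute for attribution, and the fix needs both.

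Finally, Section 7.4 covers recording, grading and attribution of perioperative events, not their tabulation, so their presence in one common table is an inference. It is the natural one, since Section 10.1 sets one window and no separate table is planned.

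**Conclusion.** The point holds as a modest improvement to descriptive tables of a secondary endpoint. In the by-grade table of Section 8.3.1, a higher-grade postoperative recurrence replaces the grade seen during dosing, so that table mixes surgical and on-drug severity over a window that is about half postoperative. In the causality summary of Section 10.4.1, loss of a drug-related event is possible but not prescribed. The gap is that the plan does not say which occurrence sets attribution.

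The size is unknown. The 0.2 to 1.8 men per term, and the 12% to 35% of on-drug grades replaced, rest wholly on assumed rates and show only that one or two men out of 20 is conceivable for a term common to both periods. The conclusion assumes that perioperative events enter the same tables. Frequency counts by term are unaffected, and no power, alpha or stopping boundary depends on the point.

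**What to change.** In Sections 8.3.1 and 10.4.1:
- Apply the once-per-patient, worst-grade rule separately in two periods: first dose to the start of surgery, and surgery to postoperative day 60.
- For the drug-related summary, take for each patient and term the worst grade among occurrences scored Possible, Probable or Definite.
- Report the two period tables together with the combined table. The postoperative table should not be demoted, because the synopsis makes non-interference with prostatectomy part of the safety hypothesis.
- Define treatment-emergent so that it matches the window in Section 10.1.

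The cost is a few sentences and one extra table. Attributions are already collected and the visit schedule places events relative to surgery, so no new data collection is needed. The downside is that a man may appear in both period tables for the same term, so the two counts do not add up to the combined one. A footnote should say so.

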8.3.2 Markers of cell proliferation

TMAs from fixed tumor samples will be analyzed for the degree of tumor cell proliferation using the validated marker, Ki-67. This will be achieved by immunohistochemical staining (30, 31), using the Ki-67 monoclonal antibody (Dako North America, Carpineteria, CA). Quantification of staining percentage will be performed using the Aperio ScanScope[®] CS instrument (Aperio Technologies, Vista, CA) as described in Section 8.3.3. This endpoint will be expressed as the mean staining percentage in tumor tissue. Assays will be performed in the laboratory of [name].

8.3.3 CD8⁺ T cell infiltration

To assess the immune response to DUPILUMAB, we will quantify the extent of CD8⁺ T cell infiltration into the prostate from harvested prostate glands. This will be done using immunohistochemical staining methods. This endpoint will be expressed as the mean CD8⁺ T cell staining percentage in harvested tumor

tissue. We will also attempt to quantify prostatic CD4⁺ T cell infiltration and T_{reg} infiltration, as well as to determine the CD8/ T_{reg} ratio and the CD4/ T_{reg} ratio.

Analysis of this endpoint will be achieved by preparing tissue microarrays (TMAs) using the highest-grade/largest tumor per patient and sampling it with 100-fold redundancy (28-31). All tissues will first be fixed in 10% neutral buffered formalin and processed into paraffin blocks. For each immunohistochemical stain (*e.g.* CD8⁺ T cell stain, CD4⁺ T cell stain, T_{reg} stain), TMA slides will be scanned using the Aperio ScanScope[®] CS instrument (Aperio Technologies, Vista, CA) and TMA cores will first be assigned a diagnosis by the study pathologist and will then be subjected to semi-automated image analysis using the Aperio system. For each biomarker, we will divide the area of brown DAB staining by the area of epithelial cells on the TMA core, obtaining a staining percentage. The area of epithelium will be obtained on each TMA core by staining with cytokeratin-8 and using automated image analysis. Cores with both tumor and normal tissue will be excluded if they contained >10% of the other component.

For CD8 staining, slides will be steamed for 20 minutes in citrate antigen retrieval solution (Vector Laboratories, Burlingame, CA) followed by incubation with a mouse monoclonal anti-CD8 antibody for 45 minutes at room temperature (Dako, Carpinteria, CA). For CD4 staining, slides will be steamed for 40 minutes in high pH antigen retrieval solution (Dako, Carpinteria, CA) and then incubated with a mouse monoclonal anti-CD4 antibody for 45 minutes at room temperature (Serotec, Kidlington, UK). For T_{reg} analysis, cells will be stained for the FoxP3 protein by steaming slides for 40 minutes in high pH antigen retrieval solution (Dako, Carpinteria, CA) and incubating them with a mouse monoclonal anti-FoxP3 antibody for 45 minutes at room temperature (eBioscience, San Diego, CA, 1:1000 dilution). In all cases, poly-HRP-conjugated anti-mouse IgG Ab (Dako, Carpinteria, CA) will be used as the secondary antibody. Staining will be visualized with diaminobenzidine (Sigma, Saint Louis, MO) and slides will be counterstained with hematoxylin.

Images of each TMA core will be captured by automated scanning of TMA slides using the Aperio ScanScope[®] CS instrument (Aperio Technologies, Vista, CA). Captured images will be imported into the TMAJ Images Application program (http://tmaj.pathology.jhmi.edu). Histological diagnoses (normal, atrophy, prostatic intraepithelial neoplasia, cancer) will be applied to all images used for the analyses by a pathologist. In addition, for TMA spots containing more than one type of lesion, the percentage of each diagnosis will be noted. All images and data will be available for viewing/downloading at

8.3.4 Regulatory T cell (T_{reg}) infiltration

The method for quantifying T_{reg} density from harvested prostate tissue is as described in Section 8.3.3. This endpoint will be expressed as the mean staining percentage in tumor tissue.

8.3.5 CD4⁺ T cell infiltration

The method for quantifying CD4⁺ T cell density from harvested prostate tissue is as described in Section 8.3.3. This endpoint will be expressed as the mean staining percentage in tumor tissue.

8.3.6 Pathological complete responses (pCR)

This will be defined as the absence of tumor identification by the study pathologist on standard histological analysis of the resected prostate specimens. The endpoint will be expressed as the proportion of men achieving a pCR.

8.3.7 PSA response rates

This will be defined as the proportion of patients who achieve an undetectable PSA (<0.1 ng/mL) by 3 months after prostatectomy. The endpoint will be expressed as the proportion of men achieving a PSA response.

8.3.8 Time to PSA recurrence

This will be defined as the interval from the time of prostatectomy to the time when the serum PSA is ≥ 0.2 ng/mL. PSA will be measured every 3 (±1) months during the first post-operative year and every 6 (±2) months during the second and third post-operative years. For subjects who have not yet demonstrated PSA relapse at the time of censoring, patients will be censored at the date of the last assessment that shows a lack of PSA recurrence. This outcome will be expressed as a median and will be determined using the Kaplan-Meier method.

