4.2 Expected Enrollment

A total of 20 patients will be included in this study. The first patients are expected to be enrolled in August 2018, once the protocol has been approved by the IRB. With an estimated enrollment rate of 2-3 patients per month, accrual is expected to be completed in 10 months.

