5.5 Follow-Up Evaluations

Follow-up visit scheduled for 30 days and 60 days after radical prostatectomy may occur in the outpatient clinic or by telephone interview. Required evaluations during this follow-up visits are listed below. Patients should then continue to be followed by their treating urologist according to standard institutional practices.

- performance status
- review of medication list
- review of toxicity/adverse events

Patients withdrawing from the study early because of adverse events should be followed until the adverse event has either resolved or stabilized. Reasons for premature withdrawal should be determined and documented.

In addition, patients will be required to have a structured assessment of post-operative PSA measurements for 3 years. In the first year after prostatectomy, PSA will be measured every 3 months (±1 mo). In the second and third years after prostatectomy, PSA will be measured every 6 months (±2 mo). These PSA measurements may be obtained outside of Johns Hopkins, but the results need to be made available to the study team.

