- **CD4⁺ T cell density.** The methods for quantifying and analyzing CD4⁺ T cell infiltration will be similar to those described for CD8⁺ T cell infiltration. Descriptive statistics and graphical summaries will be provided.
- Pathological complete responses (pCR). This will be defined as an absence of tumor identification on standard histological analysis of the resected prostate specimens.
- **PSA response rates**. This will be defined as an undetectable PSA (<0.1 ng/mL) at 3 months after prostatectomy. The proportion of patients achieving a PSA response will be compared between treatment arms using the Mantel-Haenszel test.
- Time to PSA recurrence. This will be defined as the interval from prostatectomy to the time when the serum PSA is ≥0.2 ng/mL. For subjects who have not yet demonstrated PSA recurrence at the time of censoring, patients will be censored at the date of the last assessment that shows a lack of PSA recurrence. For each treatment arm, the median time to PSA recurrence after prostatectomy (*i.e.*, the median PSA-recurrence-free survival) will be estimated with 95% confidence intervals using Kaplan-Meier survival analysis. Comparisons will be sought using the log-rank test, stratified by Gleason score.

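### The only estimate planned for time to PSA recurrence is a Kaplan-Meier median with 95% CI; in 20 men followed for 3 years the interval will usually be open-ended and the median may not be reached

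*Combined protocol and SAP*

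**What the plan says.** Section 8.3.8 defines the endpoint as the "interval from the time of prostatectomy to the time when the serum PSA is ≥ 0.2 ng/mL". Men without recurrence are handled as follows: "patients will be censored at the date of the last assessment that shows a lack of PSA recurrence". The summary measure is then fixed: "This outcome will be expressed as a median and will be determined using the Kaplan-Meier method".

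Section 10.2.2 repeats the median, which "will be estimated with 95% confidence intervals using Kaplan-Meier survival analysis", and adds: "Comparisons will be sought using the log-rank test, stratified by Gleason score". That paragraph is worded as if there were several arms, but Section 5.1 describes a single-arm study.

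On size and duration, Section 4.2 states: "A total of 20 patients will be included in this study". Section 5.5 states: "patients will be required to have a structured assessment of post-operative PSA measurements for 3 years". The visit schedule in 8.3.8 is "PSA will be measured every 3 (±1) months during the first post-operative year and every 6 (±2) months" in years two and three.

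Neither section names a recurrence-free proportion at a fixed time, and neither covers a median that is not reached. The endpoint is listed under the secondary endpoints in 8.3, but not among the objectives in 1.2 or in the synopsis list of endpoints.

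**The concern.** A Kaplan-Meier median exists only if the curve falls to one half while men are still being followed. Its upper confidence limit exists only if the upper confidence band also falls to one half, which takes many more events. PSA collection ends at 3 years and there are only 20 men, so neither is assured.

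The log-rank test in 10.2.2 does not fill the gap. It has no comparator in a single-arm trial and gives no estimate. The two neighbouring endpoints, pathological complete response and PSA response, are expressed as proportions and can always be estimated; this one cannot.

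What is at stake is modest. Each man is asked for three years of PSA tests. If the median is not reached and no time point was named in advance, any fixed-time figure reported later will have been chosen after the curve was seen.

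**Working it through.** The plan gives no figure for this endpoint to reproduce. The sample size rests on the paired t-test for M2-TAM infiltration; that power reproduces (81.1%, two-sided 5%, n = 20, effect size 0.67) but has no bearing here.

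**Inputs from the documents.** n = 20 (4.2); PSA visits at months 3, 6, 9, 12, 18, 24, 30 and 36 (8.3.8); event at the first PSA of 0.2 ng/mL or more (8.3.8); censoring at the last recurrence-free assessment (8.3.8).

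**Assumptions.** The true 3-year recurrence risk p is not given, so a range of 20% to 70% is shown. Loss to PSA follow-up is not given, so 0%, 10% and 20% by 3 years are tried.

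**Step 1: when is the median reached?** With complete follow-up, S(36) = 1 − e/20, where e is the number of recurrences. S(36) ≤ 0.5 requires e ≥ 10, so the probability is P(X ≥ 10) with X ~ Binomial(20, p).

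**Step 2: when is the upper 95% limit finite?** The upper log-log bound on S(36) must be 0.5 or less. The bound is exp{−exp[ln(−ln S) − 1.96·se/(S·|ln S|)]}, with se = √(S(1 − S)/20).

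- e = 14: S = 0.30, se = 0.1025, upper bound 0.501, so no finite limit.
- e = 15: S = 0.25, upper bound 0.449, so the limit is finite.

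The plain Greenwood bound also needs 15 events (0.501 at 14, 0.440 at 15); the log bound needs 16. The probability for the log-log bound is therefore P(X ≥ 15).

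| Assumed 3-year risk | Median reached, P(X ≥ 10) | Upper limit finite, P(X ≥ 15) |
|---|---|---|
| 20% | 0.3% | 0% |
| 30% | 4.8% | 0.004% |
| 40% | 24.5% | 0.16% |
| 50% | 58.8% | 2.1% |
| 60% | 87.2% | 12.6% |
| 70% | 98.3% | 41.6% |

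The median is as likely as not to be reached when the risk is about 47.5%. Under a convention that requires the curve to fall below one half, 11 events are needed, and the probabilities at 30%, 40%, 50% and 60% become 1.7%, 12.8%, 41.2% and 75.5%.

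**Step 3: loss to follow-up.** This was simulated with 20,000 trials per scenario, exponential recurrence times, detection at the scheduled visits and log-log limits. With 20% lost by 3 years, the median is reached in about 4%, 20%, 50% and 80% of trials at risks of 30%, 40%, 50% and 60%. Across 0 to 20% loss, the upper limit is finite in 0% of trials at 30%, under 0.5% at 40%, 2 to 4% at 50%, 13 to 16% at 60% and 42 to 46% at 70%.

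**Step 4: what the same data give at a fixed time.** Suppose 6 of 20 men recur by 36 months and follow-up is complete. The recurrence-free proportion is 14/20 = 70%, with log-log 95% CI 45% to 85% (exact binomial 46% to 88%). With 4, 8 or 10 recurrences it is 80%, 60% or 50%, with exact 95% CI 56% to 94%, 36% to 81% or 27% to 73%. The intervals are wide, but both ends exist in each case.

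**The case against.** A reader might infer that the trial can rarely supply the median, or that the endpoint will usually yield no usable number. The documents support neither reading.

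- **The recurrence risk is unknown.** Above roughly 47.5% the median is more likely reached than not. The target population in 3.1 is NCCN high or very high risk, although the listed criteria also admit Gleason 7 and stage T1c. No rule covers a PSA that never falls after surgery; under 8.3.8 such a man would count as an early event, which raises the event rate. A risk near or above 50% cannot be excluded.
- **An unreached median is still informative.** With 6 of 20 recurrences, the log-log lower bound on S(36) is 0.45, below one half. The lower 95% limit of the median therefore falls within follow-up and would be reported beside a median not reached. The Kaplan-Meier curve also remains.
- **Nothing bars a fixed-time estimate.** It could be read from the curve, and 10.5.1 allows descriptive statistics with 95% CIs where appropriate. The gap is that no time point is prespecified.
- **The alternative is not perfect.** Month 36 is the edge of follow-up. 8.3.8 allows two months either side at late visits (the Study Calendar column heading says one month), and men are censored at their last recurrence-free assessment. A man last seen at month 34 is censored before 36, so the interval in Step 4 is a best case.
- **Little hangs on it.** No decision, sample size or stopping rule depends on this endpoint.

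All of this stands as a limit on how strongly the point can be put. It does not answer the narrower point, because the upper limit is seldom finite over most of the plausible range and no other estimate is planned.

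**Conclusion.** The point holds in a limited form. The median with its 95% CI is the only estimate planned, and a two-sided bounded interval is unlikely. With complete follow-up its probability is at most about 13% for 3-year risks of 30% to 60%, rising to about 16% with 10 to 20% loss. Even at 70% risk it stays below one half. Whether the median itself is reached is open: about 5%, 24%, 59% and 87% at 30%, 40%, 50% and 60%.

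These figures assume that all 20 men have surgery and PSA follow-up and that their recurrences are independent with a common risk; the simulation with losses also assumes exponential recurrence times. The recurrence risks are assumptions throughout. The finding is minor: it concerns a secondary endpoint and has no effect on the primary analysis.

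**What to change.** In 8.3.8 and 10.2.2, make the main summary the Kaplan-Meier PSA-recurrence-free proportion at 12, 24 and 36 months, with log-log 95% CI and the number at risk at each time. Report the median and each of its confidence limits where they are reached, and state otherwise that they were not.

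The cost is one sentence in each of two places. It needs no extra patients, visits or tests, since all three times are already scheduled PSA assessments. The one drawback is that visit windows and censoring at the last assessment may leave few men at risk at 36 months. Showing the number at risk makes that visible, and the 12- and 24-month estimates are less exposed to it.
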